1.3 Hypothesis and Study Aims

The overarching hypothesis is that VTEL high-intensity functional circuit exercise in older HIV+ Veterans will improve the advanced aging phenotype and attenuate DNAm epigenetic processes underlying aging. We will explore the use of DNAm Age as an innovative biomarker that can predict adaptation to exercise by testing its association with exercise outcomes. Our experimental approach includes a 12-week VTEL exercise intervention in 80 older HIV+ Veterans who are randomized to exercise or standard of care sedentary control groups with the specific aims:

AIM 1. To determine the effect of VTEL exercise compared to control on:

- 1.1 Cardiorespiratory fitness, anaerobic threshold, and O₂pulse based on gas exchange at peak exercise
- 1.2 Sarcopenia defined by the European Working Group on Sarcopenia⁴⁴
- 1.3 Frailty defined by the Fried Phenotype⁴⁵ and the Veterans Aging Cohort Study (VACS) Index²⁷

AIM 2. To investigate the effect of VTEL exercise on DNAm Age²⁰ as a biomarker of advanced aging

AIM 3. To determine the effect of VTEL exercise on systemic inflammation by measure of:

- 3.1 DNA methylation of genes encoding pro-inflammatory cytokines in leukocytes (transcriptional regulation)
- 3.2 Corresponding systemic levels of pro-inflammatory cytokines IL-6 and IL-18 (protein expression)

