Program coordinator	Salem VAMC (50%)	Responsible for overall oversight of the project which includes: 1) monitoring numbers for recruitment, enrollment, and completion; 2)

		maintenance of current Manual of Operations; 3) providing template SOPs and CRFs to enrollment sites; 4) coordinating calls and meetings; 5) conducting audits of CRFs and protocol deviations to assess and correct inconsistencies between sites and coordinators; 6) reporting and correspondence to Salem VAMC regulatory committees; 7) maintenance of the Salem protocol regulatory study binder
Exercise physiologist	Salem VAMC (50%)	1) conduct VTEL exercise per protocol; 2) instruct and supervise participants during all exercise sessions, including maintenance of exercise training logs and HR data; 3) coordinate VTEL classes with staff at AVAMC and BVAMC
Data manager	Salem VAMC (25%)	1) oversee data collection and entry, including data QA/QC; 2) design and maintain databases located on Salem VAMC server and VINCI (REDCAP); 3) conduct data analysis and generate tables and figures

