Analyses will include participants who drop out before completion of the 12-week intervention period by way of multiple imputation. This intention to treat approach will investigate factors that may affect compliance and difficulty with exercise training, including soreness and medical comorbidity. If the pattern of missing data is missing completely at random, or simply at random, our multiple imputation should eliminate bias due to loss to follow-up. Because the participants will be recruited from clinic-based VA cohorts, we will be able to obtain clinical data from participants who drop out of the study, but remain in clinical care, to determine if drop-out was related to medical conditions that may influence outcomes. Thus, we will be able to estimate bias introduced by loss to follow-up. If there is sufficient information, we may be able to model the drop-out process and adjust our analyses for loss to follow-up even if the missing data pattern is non-ignorable. If 36 training sessions cannot be completed in 12 weeks, then total training time will be tracked, and incorporated into the data analysis.

DNA Methylation (AIM 3): We will examine the change of methylation levels after 12 weeks for each candidate marker using ANOVA models. To examine epigenetic association with each outcome, we will fit the linear regression model as follows: where Y_i is the quantitative outcome measurement, Z_i is the vector of covariates including age, race, smoking status and leukocyte proportions, and E_i is the candidate epigenetic marker. ANCOVA will be used to test for between group difference by time (pre/post exercise). The candidate epigenetic markers will involve individual CpG sites previously identified and discussed in detail section D4c. We will extend this linear regression model to account for batch/chip effects and

longitudinal measures using a linear mixed model. We will adjust the significance threshold for multiple testing using Bonferroni correction ($p < 0.05 / \text{number of tests}$).

Sample Size Estimates:

AIM 1. Paired t-test was used to test for a mean change given a range of correlation between pre and post values with assumptions of $\alpha = 0.05$ and 80% power. (Mean (SD) values for the VO_2peak are from our current high-intensity AEX + RT trial in HIV+ Veterans (Table 3). Data for 2-minute step test are from our VTEL Gerofit exercise program (C3). Values for chair stands are results from a 10-week RT in older men.⁴⁶ We will have adequate

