3 STUDY METHODS

3.1 Study Design

This study is a multi-site exercise intervention for Veterans receiving care at the Atlanta and Baltimore VAMCs that will randomize approximately 80 participants (40 per site) at these VAMCs, herein referred as enrollment sites. The intervention is 12-weeks of high-intensity functional circuit exercise performed 3 times weekly in a supervised group setting. Exercise training will be led by an exercise physiologist at the Salem VAMC (coordinating site) and broadcast to the enrollment sites. HIV-infected Veterans 50 years of age and older will be enrolled at the Atlanta and Baltimore VAMCs. Eligible participants will be randomized to exercise training (N=40) or control (N=40) groups. All participants will undergo baseline testing and follow up testing after 12 weeks at their respective enrollment site. Participants in the Control Group will be instructed to maintain their baseline sedentary lifestyle (as defined in eligibility criteria) during the 12-week intervention period. After follow-up testing is complete, participants in the control group will have the option of completing 12-week exercise training (delayed entry exercise) which will be a combined home and center-based exercise program. Pre-post exercise testing will be conducted in these participants to gauge individual progress and provide individual feedback that is a benefit of study participation, but these results will not be part of the randomized trial analyses.

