Feasibility of the project is supported by investigators with a track record of collaboration and the existing infrastructure including experience staff, well-defined population, and available exercise, VTEL, and lab equipment. Based on prior exercise trials we have conducted in this population, we expect a 33% eligibility failure rate and a 30% attrition rate. Due to the COVID hold in 2019-2000, first study year, no participant activity occurred and a 1-year cost-extension has been awarded which will allow for completion of 40 participants per site to complete the exercise trial within the project period (Table 5).

Table 5	Y 2				Y 3				Y 4				Y 5				total
	1	2	3	4													
Quarter	1	2	3	4	1	2	3	4	1	2	3	4	1	2	3	4	
Completers	2	6	6	6	6	6	6	6	6	6	6	6	6	4	2		80
AVAMC	1	3	3	3	3	3	3	3	3	3	3	3	3	2	1		40
BVAMC	1	3	3	3	3	3	3	3	3	3	3	3	3	2	1		40

Eligibility

HIV+ adult men and women of all races and ethnicities who are 50 years of age and older will be eligible. Eligibility criteria are based on our exercise research in older HIV+ adults and American College of Sports Medicine guidelines and are designed to minimize attrition, maximize safety, and limit confounding

factors. Of note, smoking is not an exclusion criterion since approximately 70% of the otherwise eligible HIV+ Veterans are smokers, and if excluded would decrease the study's generalizability.

Inclusion Criteria: Participants will be on antiretroviral therapy with HIV viral suppression because HIV viremia affects DNA methylation and DNA age. Only sedentary adults will be eligible (not engaging in structured activity for exercise ($\geq 1/\text{week}$)).

Exclusion Criteria: Specific eligibility criteria are listed in Table 6 below and include objective cut-off limits designed to maximize safety and minimize attrition but not prohibitively limit enrollment and maintain generalizability. Eligibility will be determined by information collected by a clinician study investigator during the eligibility visit which occurs after informed consent is obtained. The eligibility visit includes history and physical exam (H&P), review of the electronic medical record, and resting ECG. The following eligibility checklist was used for IRB submission at the enrollment sites:

Table 6. Eligibility Checklist		
*based on date of H&P		
Inclusion Criteria		
Yes	No	
		Veteran living with HIV and under care at VAMC
		50 years of age and older
		Stable antiretroviral therapy (ART) (same ARV medications within 3 months)

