Compensation will be allocated directly at each site, per their local policies and procedures. Each site has the same target completion rate and annual participation reimbursement budget, but will be allowed to adjust reimbursement per study procedure as deemed appropriate per local standards. Participant name, address, social security number, and amount of payment will be submitted to the Internal Revenue Service for tax reporting purposes for any financial compensation they receive per calendar year as a result of participation in this research study. The Salem VAMC team will not have access to this information. All participants are reimbursed for baseline and follow-up testing. For performance of VTEL exercise training, reimbursement is provided per exercise session for travel cost and a completion bonus at end of 36 sessions (VTEL intervention group). The delayed exercise control group will complete follow-up testing at 24-weeks in addition to 12-weeks, and therefore total study reimbursement will be greater. During the delayed exercise period, the control group will be reimbursed for the weekly phone calls and monthly in-person group visits.

Use of research samples may lead to inventions or discoveries that could become commercially valuable. In the event of scientific discoveries made using participant samples, study participants will not receive compensation or profits from any inventions, discoveries, or products.

References

3. Deeks SG. HIV Infection, Inflammation, Immunosenescence, and Aging. *Annu Rev Med.* 2010.
5. [name] KK, Sorkin JD, Smith BA, Katzel LI. Reduced aerobic capacity and physical functioning in older HIV-infected men. *AIDS Res Hum Retroviruses.* 2006;22(11):1113-1121.

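### About 80 randomised, 30% expected attrition and 80 planned completers cannot all hold; if the 30% falls after randomisation, about 56 complete

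*Combined protocol and SAP*

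**What the plan says.** The number randomised is given consistently. Section 1.3 describes the intervention "in 80 older HIV+ Veterans who are randomized to exercise or standard of care sedentary control groups". Section 3.1 says the study "will randomize approximately 80 participants (40 per site" and then "Eligible participants will be randomized to exercise training (N=40) or control (N=40) groups". No section gives a randomised number above about 80.

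Section 3.3.a (Enrollment and Completion Targets) states "we expect a 33% eligibility failure rate and a 30% attrition rate". The next sentence says that a one-year extension "will allow for completion of 40 participants per site to complete the exercise trial within the project period (Table 5". Table 5 then schedules completers by quarter, to a total of 80, with 40 at each site.

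Section 2.3.e accepts that people will leave after randomisation: "Analyses will include participants who drop out before completion of the 12-week intervention period by way of multiple imputation". Its sample size text allows 40% attrition for Aim 1 and 28% for Aim 2 without saying from what number. It calls 34 participants sufficient for Aim 3 with no attrition allowance.

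Completion is also something the study tracks. Table 2 (section 2.2.c) makes the program coordinator responsible for "monitoring numbers for recruitment, enrollment, and completion", and section 3.3.f says "Each site has the same target completion rate and annual participation reimbursement budget".

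**The concern.** The same figure, 80 in total and 40 per site, serves both as the number who start and as the number who finish, next to a forecast that 30% will be lost. At least one of the three statements must be wrong or mislabelled.

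Two things are at stake. First, a site that randomises its 40 and loses exactly the forecast share ends 12 completers below its Table 5 figure, so monitoring against that table cannot tell expected loss from a real retention problem. Second, the number who complete is what the sample size statements in section 2.3.e depend on. A reader who takes 40 completers per site at face value will also assume 40 per arm with complete data, and will misjudge which of those statements hold at the forecast loss.

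**Working it through.** **Inputs.** Randomised: 80, 40 per site, 40 per arm (sections 1.3, 3.1). Attrition 30%, eligibility failure 33%, and Table 5 (section 3.3.a). Required sizes and attrition allowances (section 2.3.e). Equal loss by site and by arm is my assumption; the documents give no split.

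**1. Table 5 as printed.** Total: 2 + 12 x 6 + 4 + 2 = 80. Per site: 1 + 12 x 3 + 2 + 1 = 40. The table is internally correct and agrees with the sentence above it. (The text copy shows 15 quarterly values under 16 quarters; since the sums match the totals, nothing turns on this.)

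**2. Expected completers** = randomised x (1 - attrition after randomisation).
- All 30% after randomisation: 80 x 0.70 = 56; per site or per arm, 40 x 0.70 = 28. Gap to Table 5: 80 - 56 = 24, or 12 per site.
- As an illustration, 15% after randomisation: 80 x 0.85 = 68.
- None after randomisation: 80. This is the only case that gives Table 5, and section 2.3.e does not expect it.

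Eligibility failure does not close the gap. It is listed separately and acts before randomisation: 80/0.67 = 119.4, so about 119 consented yield 80 randomised.

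**3. Which number comes before attrition?** The Aim 2 arithmetic helps. The plan's means differ by 68.7 - 62 = 6.7 years, with SDs 10.8 and 10. The standardised change is 6.7 / sqrt(10.8² + 10² - 2 x r x 10.8 x 10) = 0.544, 0.643 and 0.828 at r = 0.3, 0.5 and 0.7. A two-sided paired t-test at alpha 0.05 and 80% power needs 29, 21 and 14, exactly the plan's figures. Then 40 x (1 - 0.28) = 28.8, or about 29. From a base of 80 the same allowance would leave 57.6, and 28% would be an odd limit to name. So the Aim 2 sentence appears to take 40 per arm as the number before attrition.

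**4. The sample size statements at 28 per arm.**

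| Aim | Stated need | Stated allowance | Left from 40 at that allowance | At 30% loss (28) |
|---|---|---|---|---|
| 1 | at most 16 | 40% | 24 | covered |
| 2, r = 0.3 | 29 | 28% | 28.8 | 1 short; power 79.2% (80.7% at 29) |
| 2, r = 0.5 / 0.7 | 21 / 14 | not stated | – | covered |
| 3, if exercise arm | 34 | none | – | 6 short |

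For Aim 3, 1 - 34/40 = 15% is the most that an arm of 40 can lose, half the forecast. If 34 meant all completers, 56 would cover it.

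**5. Keeping 80 completers instead.** 80/0.70 = 114.3, so 115 randomised, or 116 for equal arms (116 x 0.70 = 81.2). That is 36 more than 80. Consented: 116/0.67 - 80/0.67 = 173.1 - 119.4 = 53.7, about 54 more.

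**The case against.** The strongest reply is that the documents do not say outright which figure is wrong. The subsection heading speaks of completion targets, the table row is labelled as completers, and the sentence ties 40 per site to the extension. On that reading 80 completers is the goal and the randomised number is too low. This deserves weight, but two sections give 80 as the number randomised, no section gives a larger one, and the Aim 2 allowance works from 40 per arm. *Approximately* 80 cannot stretch to 115, which is 44% more.

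A second reply concerns timing. Section 3.2.b randomises after baseline testing, and section 3.3.b allows up to 5 weeks from the eligibility visit for that testing, so part of the 30% could be lost before randomisation. This stands: 56 is the lower end of a range, not a fixed figure. It does not rescue 80, which still needs zero loss afterwards.

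Third, the effect is modest, and no section attaches a consequence to missing Table 5. That also stands.

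A reader might go further and infer that the trial is too small for its stated aims. This discrepancy does not show that. Aim 1's stated sizes are met with room to spare, and the Aim 2 shortfall is one participant at the lowest correlation only, which is immaterial. The Aim 2 sentence is also true as written, because it is conditional on 28%. A reader might equally infer that recruitment must rise to 115; nothing in the documents calls for it.

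On Aim 3 one could argue that 34 names no arm and is met by 56 completers overall. But section 2.3.e describes a one-sample paired calculation for a change with exercise, which most naturally means the exercise arm.

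**Conclusion.** The contradiction is certain: 80 randomised, 30% attrition and 80 completers agree only if nobody is lost after randomisation, and the plan expects loss. The size is conditional. If the 30% applies after randomisation, completers are about 56 against 80 stated, a gap of 24 (12 per site), with about 28 per site and per arm under equal loss. If some of it falls earlier, completers lie between 56 and 80.

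For inference, the one statement that needs qualifying is Aim 3's: if its 34 refers to the exercise arm, about 28 completers do not meet it. The point concerns a stated target and that sufficiency statement, not the design or the analysis. I rate it minor to moderate.

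**What to change.** Keep 80 as the number randomised. In section 3.3.a, state that the 30% applies after randomisation, if that is what is meant. Then correct the sentence and the table together, in one of two ways:

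- Restate completers as about 56 (about 28 per site) in the sentence, and revise the quarterly cells and both site rows of Table 5 so that they sum to it. Changing only the total would leave cells that add to 80.
- Relabel the Table 5 row as randomised, and change the sentence to say that 40 per site will be randomised with about 28 per site expected to complete. Relabelling alone would leave the conflicting sentence. The quarters should also be checked, since a participant is randomised about 12 weeks before completing.

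In section 2.3.e, state the base (40 per arm, if so) for the Aim 1 allowance of 40% and the Aim 2 allowance of 28%. Say whether the Aim 3 figure of 34 refers to the exercise arm; if it does, note that it allows 15% attrition and qualify the sufficiency statement for about 28 completers.

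The cost is one table, one or two sentences in section 3.3.a and three in section 2.3.e. No new power calculation is needed, and recruitment and analysis are untouched. Raising randomisation to 115 or 116 to keep 80 completers would mean 36 more randomised (at 116) and about 54 more consented, and is not recommended.

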A Garmin Connect web account will be generated by research staff for the participants in the delayed entry exercise group. The account, including user ID and password, will not include any element of PHI or PII. Individual-level data is limited to heart rate, height, weight, sex and year of birth. For any individual over the age of 85, year of birth will be set at 1930. Data from the Garmin activity tracker device will be uploaded from the wrist tracker to the Garmin Connect web site via the app installed on each participant's personal cell phone. Location tracking on the Garmin app will NOT be enabled on the phone. Data from the Garmin device will be temporarily stored on the Garmin commercial server (<https://connect.garmin.com/en-US>) (TLS 1.2, AES with 256-bit encryption (High); ECDH_P256 with 256 bit exchange). The file with linkage of the participant Garmin user ID to PHI will always remain behind

the VA server at all times and is never released to Garmin. Therefore, there is no PHI/PII in the storage, extraction, and transfer of data from the Garmin device, phone app, or web site.

The metabolic cart that collects gas exchange data and the DXA scan report are paper source documents. Participants are identified for both procedures by a study ID with no PHI. Scanned copies of these documents will be uploaded by the enrollment site to the Salem network folder.

All data collection and storage procedures will be approved by each respective VAMC Information Security Officer (ISO) and Privacy Officer (PO). Salem VAMC already has procedures and approval in place for current exercise studies.

2.3.e Statistical Plan

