3.2 Coordinating Center at the Salem VAMC (Research Activities Conducted at SVAMC)

3.2.a Exercise Intervention: VTEL Exercise Training

Exercise Training Description

The exercise physiologist located at the SVAMC will be responsible for conduct of all exercise training under the supervision of the PI. Exercise training will be delivered by VTEL broadcast from the Salem VAMC to participants at the Atlanta VAMC and Baltimore VAMC. In the event that the Salem EP is not available to deliver the training, the exercise training can be delivered by another experienced EP through a telehealth platform. Research staff at the Atlanta and Baltimore VAMCs will be in the room with the participant to help with heart rate monitors and portable exercise equipment, and in the event of an emergency. Rooms will be equipped with steps, hand and ankle weights, dumbbells, chairs, and bands. No stationary exercise equipment will be used in either aerobic (AEX) or resistance training (RT). The intervention consists of high-intensity circuit exercise training performed 3 times weekly for 12 weeks in a group setting. Circuit training is an exercise modality consisting of a series of exercises at different stations.

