Exercise Intensity: To ensure that *AEX intensity* is met, participants will wear Polar HR monitors (Polar, Lake Success NY) with alarm limits set by the exercise physiologist and programmed into the watch by enrollment site staff. The AEX protocol will follow exercise interventions protocols that have been successful in older HIV+ Veterans. Participants will initially train at 50% heart rate reserve (HRR), increasing target HR by 5-10% weekly until 70-80% HRR is reached. Based on our work to date, three minutes of AEX per circuit is feasible. *Resistance training (RT)* progression will also be based on our prior experience with center-based progressive high-intensity RT in HIV+ adults. This protocol involves initial weight lifting of 50-60% 1-RM in two sets of 8 repetitions with progression to 12 repetitions. Then training weight is increased by an amount (~10%) that causes the muscle group to fatigue/fail after eight repetitions. However, functional RT exercises utilize multiple muscle groups, unlike traditional RT. Therefore, we will use the number of repetitions for specific functional RT exercises as the target, based on thresholds set by Rikli and Jones. The use of hand and ankle weights and multiple muscle engagement will help provide higher intensity RT. Strength exercises will be performed until muscle fatigue at three stations of the circuit with each strength exercise performed quickly.

Treatment Fidelity: The exercise physiologist will maintain a training log for each exercise session for each participant. The log includes the type of each RT exercise and number of sets, the type and duration of each AEX exercise, and any special participant feedback or concern. The heart rate will be measured and recorded continuously using a chest-strap heart rate monitor (Polar Electro Inc., Lake Success, NY) and downloaded by the

enrollment site staff at their site. The exercise physiologist will compile and review weekly HR data on the Salem VAMC shared folder to document AEX duration and intensity. The exercise physiologist will meet weekly with [name] to ensure interim training targets are met for each participant. In addition,

Table 4. Circuit Exercises by Modality

Circuit	AEX (Target HR)	RT (8-12 reps)
1	Step Ups	Bicep curls
		Chest Press
		Lateral Shoulder Raise
2	Shadow Boxing	Romanian Dead Lift
		Side Bends
		Calf Raises
3	Step Ups	Squat
		Reverse Wood Chop
		Bent Over Row
4	Lateral Side Steps	Lateral Band Walk
		Triceps Extension
		Wide Pull

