Ventilator Threshold. Rationale: The onset of anaerobic metabolism or anaerobic threshold (AT) is an estimate of submaximal exercise capacity and can be measured in several ways. We will use ventilatory threshold (VT) as a well-described clinical estimate of AT that has a high test-retest reliability in adults with chronic disease.⁶⁵ Method: VT will be derived from two different plots including using V-slope method and ventilatory equivalents. O_2 consumption at VT and the percentage of VTO_2/VO_2 peak will be determined.

Dual-energy X-ray absorptiometry (DXA): Participants will undergo a DXA after an overnight fast. Total and regional lean tissue mass and bone density will be measured. Change in muscle mass and adiposity will be calculated and tested for between group differences.

Appendicular skeletal mass index (ASMI): ASMI will be calculated as lean appendicular mass/height².

Established cut-offs for ASMI measured by dual-energy X-ray absorptiometry (DXA) will be used to define low muscle mass.^{66,67} ASMI predicts clinical outcomes in diverse patient populations.^{68,69}

Adiposity: total, truncal, and appendicular fat mass and percent body fat

Functional Performance Testing Battery: Function tests will include standard measures of functional performance. Body circumferences (waist, hip), weight, and height will be measured using the protocol established in the Third National Health and Nutrition Examination Survey. We have performed this set of physical function tests on over a hundred HIV-infected adults and expect it to take 20-30 minutes to complete. Function testing will take place in the Baltimore and Atlanta VAMCs with VTEL supervision by the Salem VAMC exercise physiologist to ensure testing accuracy.

Lower extremity strength by timed chair stands: Rationale: The 30-second chair stand correlates with 1-RM leg-press performance in older men ($r = .78$)⁷⁰ and predicts mobility disability⁷¹ and mortality.¹⁵ The test-retest reliability is 0.89.⁷¹ Method: The number of times is counted within 30 seconds that a participant can rise to a full stand from a seated position without arm assistance.

Upper extremity strength by timed arm curl: Rationale: The 30-second arm curl test correlates with 1-RM biceps strength ($r= 0.62$)⁷¹ and improves with RT.⁴⁶ Method: The number of times a hand weight can be curled through a full range of motion in 30 seconds is measured. The test-retest reliability is 0.80.⁷²

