2. Blood sampling: Risk associated with blood sampling is minimized by use of aseptic technique and an experienced and certified phlebotomist. The research coordinator is responsible for safety monitoring of this procedure.

3. Radiation exposure: Exposure is minimal for the DXA scans. Participants will be instructed, verbally and in writing in the informed consent, to notify research staff of any additional radiologic tests outside of the study. We do not expect women over 50 years of age to be childbearing, but menopause will be confirmed by history and a serum pregnancy test performed, if needed. The PI is responsible for safety monitoring.

4. Tests of functional performance: These tests involve a variety of timed walks, getting up from a chair, and tests of balance. No tests will be performed before the participant is examined by a physician. An exercise technician who is trained in CPR will be administering these tests. A crash cart and emergency medications are available in the area where these tests are performed. The exercise physiologist is responsible for safety monitoring.

5. Nutrition: The 24-hour recall allows participants to discuss their diet with research staff in a private setting and in a non-judgmental manner. The research coordinator is responsible for safety monitoring.

6. Surveys: Confidentiality will be protected by using only study ID number on the surveys and having participants complete them in a private setting.

7. Garmin wrist device: This brand and style of commercial physical activity device was chosen based on prior work with older veterans which showed it was preferred compared to other commercially available devices based on ease of use and comfort.⁸¹ The risk of minimal wrist discomfort will be minimized by appropriate sizing of the device band and the option for participants to remove the device at bedtime.

Confidentiality of data: Confidentiality of data is of concern, particularly when information includes HIV status. The investigative team has taken extensive steps to ensure the confidentiality of the data as discussed above in Data Management section. All members of the research team are responsible for minimizing loss of confidentiality of participant records, and the PI is ultimately responsible for all aspects of study conduct.

3.3.e Benefits

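### The Salem exercise physiologist role that trains the exercise arm also supervises the 12-week function tests, and no masked assessor or threshold reader is specified

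*Combined protocol and SAP*

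**What the plan says.** **Training.** Section 3.2.a: "The exercise physiologist located at the SVAMC will be responsible for conduct of all exercise training under the supervision of the PI". Table 2 (section 2.2.c) lists a single exercise physiologist post, at Salem and 50% effort, with the duty to "instruct and supervise participants during all exercise sessions, including maintenance of exercise training logs and HR data". Under Treatment Fidelity in section 3.2.a, this person meets an investigator weekly "to ensure interim training targets are met for each participant". Another experienced exercise physiologist may deliver training if the Salem one is unavailable.

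**Function tests.** Section 3.3.b places them at Atlanta and Baltimore "with VTEL supervision by the Salem VAMC exercise physiologist to ensure testing accuracy". Section 3.3.d adds: "An exercise technician who is trained in CPR will be administering these tests". The same item makes the exercise physiologist responsible for safety monitoring.

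**Threshold.** Section 3.3.b: "VT will be derived from two different plots", by the V-slope method and ventilatory equivalents. No reader is named. Section 2.3.d says of the metabolic cart and DXA reports: "Participants are identified for both procedures by a study ID with no PHI". Scanned copies go to the Salem network folder.

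**Status of the outcomes.** Section 1.1 puts anaerobic threshold in the primary objective. Section 2.3.e names the 2-minute step test beside VO₂peak as a dependent variable for cardiorespiratory fitness, and both it and chair stands are Aim 1 rows of the sample-size table. Strength enters as a component for secondary analyses.

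**Masking.** The only separation of roles described is in section 3.2.b, where the keeper of the allocation list has no study data and no contact with participants.

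**The concern.** The three function tests are counts within a fixed time. They depend on how hard the participant tries and on judging whether a stand, a curl or a knee lift was complete. Randomization follows baseline testing, so the trainer cannot know the arm at baseline. At 12 weeks the trainer has led exercise participants through up to 36 sessions and answered for their progress. The document describes no comparable contact with controls.

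Participants cannot be masked to exercise, so neutral assessment is the main protection left. Without it, warmer encouragement or more generous counting in one arm enters the treatment comparison directly. Baseline adjustment does not remove it, and a larger sample makes a fixed bias more likely to reach significance. The threshold raises a related problem: a judgement read from plots can drift if the reader knows the arm or visit, and nothing in the document prevents that.

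**Working it through.** **Where the roles overlap**

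| Outcome | Who is documented as involved | Trainer overlap documented? |
|---|---|---|
| Chair stand, arm curl, 2-minute step test | Technician administers; Salem exercise physiologist supervises by video (3.3.b, 3.3.d) | Yes |
| Treadmill test (VO₂peak, O₂ pulse) | A clinician and an exercise physiologist in the room, not identified as the Salem trainer (3.3.d) | No |
| Ventilatory threshold | No reader named (3.3.b) | Not stated; no masking specified |
| DXA measures, VACS Index, DNAm Age | Not dependent on effort at the test | Not applicable |

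**How large would a bias have to be to matter?** The plan gives no figure for supervision bias, so there is none to reproduce. The following is an illustration.

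Inputs from the plan: post-intervention SD 5.6 for chair stands and 17 for the step test; planned gains 25.4 − 17.8 = 7.6 stands and 86 − 67 = 19 steps; pre/post correlations r from 0.3 to 0.7 (all section 2.3.e). There are 40 per arm (section 3.1), or 40 × (1 − 0.30) = 28 with the expected 30% attrition (section 3.3.a).

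Assumed: exercise has no true effect, and the exercise arm alone gains b = 1 to 2 stands (1/7.6 = 13% to 2/7.6 = 26% of the planned gain) or b = 3 to 5 steps (3/19 = 16% to 5/19 = 26%).

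Formulas: ANCOVA residual SD s = SD × √(1 − r²); standard error = s × √(2/n); noncentrality = b / standard error. The rejection rate is the two-sided 5% noncentral t probability on 2n − 2 degrees of freedom. Using 2n − 3 changes nothing at this rounding.

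Worked case, chair stands, n = 28, r = 0.5:
- s = 5.6 × √0.75 = 4.85
- standard error = 4.85 × √(2/28) = 1.296
- b = 1: noncentrality 0.77, rejection rate 11.8%
- b = 2: noncentrality 1.54, rejection rate 32.9%

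| Assumed bias | r | 28 per arm | 40 per arm |
|---|---|---|---|
| 1 stand | 0.5 | 12% | 15% |
| 1 stand | 0.7 | 15% | 20% |
| 2 stands | 0.5 | 33% | 45% |
| 2 stands | 0.7 | 45% | 60% |
| 3 steps | 0.5 | 12% | 15% |
| 3 steps | 0.7 | 15% | 19% |
| 5 steps | 0.5 | 24% | 32% |
| 5 steps | 0.7 | 33% | 44% |

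At r = 0.3, the plan's lowest correlation, one stand gives 11% (28 per arm) and 13% (40 per arm), and two stands give 28% and 38%. Even the smallest assumed bias at least doubles the nominal 5%. No comparable figure can be given for the threshold, because the plan states no SD for it.

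**The case against.** The strongest reply has four parts.

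**Silence is not evidence of unmasked reading.** A reader might infer that threshold plots will be read with arm and visit known. The document does not say so. It delegates procedures to a Manual of Operations and an SOP for each procedure, and neither is in the document. This stands: the supportable statement is that no masked reader is specified.

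**Local staff are not shown to be neutral.** A reader might infer that independent testing needs no one new. The document does not support that. Site research staff are in the room during training (section 3.2.a), and the research coordinator makes safety checks before each session (section 2.3.g). The technician is not in Table 2 and is not described as separate from training. The exercise physiologist at the treadmill test is neither placed at the function tests nor said to be a site employee. This also stands, so the fix may reduce the bias without masking the tester.

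**The trainer is remote and has a stated purpose.** Supervision is by video, a technician administers, who counts is not said, and another exercise physiologist may deliver some training. The link serves accuracy, and the exercise physiologist has a safety role at these tests. This narrows the exposure but leaves the overlap. Accuracy can be served by training testers beforehand, and the safety role must remain covered.

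**The size is assumed.** This is correct. The rejection rates follow wholly from the chosen bias and from a null true effect. They show sensitivity and do not estimate what will happen.

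**Conclusion.** The point holds in limited form. The role that delivers the exercise also supervises the 12-week function tests, and the plan specifies no masked assessor for them and no masked reader for the threshold. One affected test is a named fitness outcome, and the threshold is in the primary objective, so an avoidable route to bias is left open.

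The documents do not show that bias will occur or that plots will be read unmasked. They do not place the trainer at the treadmill test, so the point does not extend to VO₂peak or O₂ pulse. On the assumption of 1 to 2 extra stands in one arm and no true effect, false positives would be about 12-45% with 28 per arm and 15-60% with 40 per arm at r 0.5-0.7. The change is worth making because it is small, not because the bias has been measured.

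**What to change.** **Function tests at 12 weeks.** State that the technician who already administers them instructs and counts to a fixed script with standardised encouragement, and that the trainer neither coaches nor scores. The trainer may train testers beforehand. Keep the safety-monitoring role in section 3.3.d covered. Where possible, the tester should not be someone who attends the training sessions.

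**Threshold.** Name a reader without access to allocation or training logs, and present the plots under a code that hides arm, visit and test date. Reports are already identified by study ID and scanned to Salem, so this adds a recoding step to an existing route. Whether the printouts show dates is not stated and should be checked. Averaging the two threshold methods is optional.

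If either change is not feasible, the protocol should say why masking is absent.

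**Cost.** SOP wording, a small recoding step and less central oversight of scoring at the test. The tester may still not be fully masked. Sample size is unaffected.
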